 - i. Boys: <https://www.cdc.gov/growthcharts/data/extended-bmi/BMI-Age-percentiles-BOYS-Z-Scores.pdf>
 - ii. Girls: <https://www.cdc.gov/growthcharts/data/extended-bmi/BMI-Age-percentiles-GIRLS-Z-Scores.pdf>
6. History of prescription for therapeutic gum chewing and/or use of edibles in treatment program
7. Previous tongue tie releases (frenuloplasty and frenectomy)
8. Any therapeutic oral device treatment
9. Previous or current treatment from any other dental, OMT or orthodontic provider
10. Gross neglect of patient's oral health and presence of dental caries
11. Grade 4 tonsils on Brodsky scale

Screening Criteria

1. Accepts Myo Munchee on first presentation
2. Tolerates initial examination including taking measurements
3. Agrees to not seek out other medical treatment for their dental or OMD issues
4. Insufficient nasal patency - proxy for enlarged adenoids - unable to complete the Rosenthal test by reaching 20 breaths through nose with mouth closed ([reference](#))

Materials

1. Myo Munchees
 - a. Mini: 1.5 years - 4 years
 - b. Junior: 4 - 8 years
2. OMT materials
 - a. Dusico Balloon
 - b. Tongue depressor
 - c. Veggie straw
3. Dental materials
 - a. iTero: <https://itero.com/en-AU>
 - b. Palatometer - image 3 - [link](#)
 - c. Caliper - <https://www.harborfreight.com/hand-tools/measuring-marking/calipers-micrometer/calipers.html>

Methods

Power Calculation

With n=12 subjects per group (1 control and 3 treatment groups), totaling 48 subjects overall, we will have at least 80% power to detect a LARGE¹ effect size (defined as mean difference relative to pooled standard deviation) of 1.2 or higher between any of the treatment groups and control group. With 6 subjects in the control group and 12 subjects in the treatment group, we will only have a power of 60% to detect an effect size of 1.2 or greater.

To have 80% power to detect a medium ($d=0.6$) effect size between any of the treatment groups and control, we would require n=45 subjects per group.

Method of treatment group allocation

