Subjects eligible for participation in the study will be randomized to either Myo Munchee only (Group A) or Oral Motor Therapy only (Group B) or Myo Munchee + Oral Motor Therapy (Group C) or Control (Group D). Permuted block randomization with block size = 12 will be carried out using the following shinyApps: <https://baker-biostats.shinyapps.io/pblockrand/>. The randomization list will be attached to the enrolment document and concealed from the investigators until patients are recruited.

Treatment Groups

Dual certified Speech Language Pathologist and Certified Orofacial Myologist for the treatment groups will see all 48 patients

Group	Patients
Group A: Myo Munchee ONLY	12
Group B: Oral Motor Therapy ONLY	12
Group C: Myo Munchee + Oral Motor Therapy	12
Group D: Control, no treatment	12
Total number of patients	48

Treatment Protocols

Myo Munchee treatment protocol

The patients in this treatment group will use the Myo Munchee. Due to patient and therapist appointment scheduling, treatment may need to be performed over a video/internet call. This will be documented in the

¹ Using Cohen's d threshold for effect size (Cohen, 1988), small effect size = 0.2, medium = 0.5, large > 0.8

appointment notes whether it was an online or video meeting. Practitioner will also assess the ability of the patient to chew the Myo Munchee during each appointment and will note this.

Parental and patient education: <https://drive.google.com/drive/folders/1gI8FREl1xU1-2jF6NQLFtHGfgMYGnyZ1>

Patient requirements: Mirror used for exercises. Body is either standing against the wall, upright and supported in a chair or lying on the floor to ensure aligned posture. All exercises are performed 6 days per week (6/7)

Myo Munchee treatment protocol:

1. 1-minute x2 per day, week 1
2. 2-minute x2 per day, week 2
3. 4-minute x2 per day, week 3
4. 5-minute x2 per day, week 4
5. 6-minute x2 per day, week 5 onwards till 6 months

Total time commitment for at-home exercises: 72 minutes per week

Total time at-home commitment for 6 months: 72 hours

Oral Motor Therapy Treatment Protocol

This treatment group involves performing the required Oral Motor Therapy exercises. Due to patient and therapist appointment scheduling, treatment may need to be performed over a video/internet call. This will be documented in the appointment notes whether it was an in-person or online/video appointment.

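### A single block size of 12, printed in the protocol of a trial with no blinding described, would let anyone who knows all earlier allocations predict some later ones: up to about 5 of 48 with certainty.

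*Protocol*

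**What the plan says.** - **Block size.** Method of treatment group allocation specifies "Permuted block randomization with block size = 12". No variation in block size and no stratification by site is stated there.
- **Size and arms.** The Power Calculation section plans four groups of 12, "totaling 48 subjects overall". The Treatment Groups table gives the same split.
- **Concealment.** The allocation section continues: "The randomization list will be attached to the enrolment document and concealed from the investigators until patients are recruited". A footnote to the Measurement and Treatment Timeline table adds that a child is allocated only once all eligibility criteria are met.
- **Visibility of the arms.** The arms are the device, the exercises, both, or "Control, no treatment". No blinding of families or therapists is described.
- **Who sees the children.** Under Treatment Groups: "Dual certified Speech Language Pathologist and Certified Orofacial Myologist for the treatment groups will see all 48 patients". The measurement timeline also places the speech-language pathologist and the dentist at T0, before allocation.
- **Entry criteria.** They combine millimetre cut-offs for the palate, signs of orofacial dysfunction, and screening items such as "Tolerates initial examination including taking measurements".

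**The concern.** Concealment has two parts: nobody sees the list, and nobody can work out its next entry. The protocol deals with the first. On the second, it tells every reader that each run of 12 children contains three per arm. Where past allocations are visible, someone keeping count can see which arms are exhausted in the current block and, near its end, which arm must come next.

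That matters if the same person can influence whether or when a child is enrolled. Some screening items, such as tolerating the examination, leave room for judgement, and the therapist role is present at T0. With 12 children per arm, a few steered enrolments could shift a comparison. The untreated arm is the most exposed, because staff could know that the remaining places in a block all bring treatment.

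**Working it through.** The protocol gives no figure for predictability, so there is none to reproduce.

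**Inputs from the protocol.** 48 children, 4 equal arms, block size 12. Hence 48/12 = 4 blocks, 12/4 = 3 places per arm per block, and 4 × 3 = 12 per arm, which agrees with the Treatment Groups table.

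**Upper case (assumption): the observer knows every earlier allocation and all blocks fill.**

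1. *Certain allocations.* An allocation is certain when all remaining places in the block belong to one arm. The last place always is. The last two match with probability 2/11, and the last three with probability (2/11)(1/10). Per block: 1 + 2/11 + 2/110 = 1.2. Over four blocks: 4 × 1.2 = 4.8.
2. *Control used up.* The third of three control places in a block of 12 falls on average at position 3 × 13/4 = 9.75. That leaves 12 − 9.75 = 2.25 places per block, and 4 × 2.25 = 9.0.
3. *Best guess.* Always guess the arm with most places left. An exact recursion over the remaining counts gives 5.287 correct per block; 4 × 5.287 = 21.1 of 48, or 44%. Chance gives 12 of 48, or 25%.
4. *At least one arm ruled out.* The same recursion gives 20.2 of 48.

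If each of the two listed sites has its own list filled to 24, there are still four full blocks and the results are unchanged. If the sites recruit unevenly and only three blocks are completed, certainty falls to about 3 × 1.2 = 3.6.

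**Lower case (assumption): two people share one list, recruit about equally, and each sees only their own site's children.** Simulation gives about 0.01 of 48 certain, 32% correct guesses, and control known to be used up for about 1 of 48.

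**Alternatives, with the same fully informed observer:**

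| Scheme | Certain (of 48) | Best guess correct | Control known used up (of 48) |
|---|---|---|---|
| Four known blocks of 12 | 4.8 | 44% | 9.0 |
| One permuted list of 48 | 1.3 | 36% | 2.8 |
| Undisclosed order of 8/12/16, totalling 48, possible sizes known | about 1.9 | about 44–45% | about 3.6 |

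For the single list, the certain count is 48/(48 − 12 + 1) = 1.30; the same formula for a block of 12 gives 12/10 = 1.2. Control used up is 48 − 12 × 49/13 = 2.77. The best guess is right for 17.2 of 48. These figures already assume that the observer knows there are 12 per arm. The varied-block row is simulated.

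**Is 12 too small?** Fixed blocks of 8 would give 6.9 certain and blocks of 4 would give 12. Twelve is not unusually small. The weakness is a single, disclosed size where allocations can be seen.

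**The case against.** The strongest objection is that the upper figures describe the best-informed guesser. A reader might infer that about 5 allocations are in fact known in advance. The protocol does not support that. It names a professional role, not one individual, for all 48 children; it lists two sites; and it does not say whether they share a list. The range from near 0 to 4.8 stands, and nothing shows that any bias has occurred.

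Second, the protocol has safeguards: the list is concealed and allocation follows eligibility. Both are real, and neither prevents inference from past allocations.

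Third, entry is not all judgement. The palatal criteria are numeric, video corroborates resting mouth posture, and nothing says that the dentist keeps track of allocations. This narrows the room for steering. It does not close it, since the therapist attends T0 and softer screening items remain.

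Fourth, a reader might infer that no analysis could repair the resulting bias. That goes too far. The primary outcomes are measured at baseline, and the Data Analysis section allows adjustment for demographic and clinical variables. Adjustment can reduce imbalance on measured factors, but not on unmeasured ones such as likely cooperation.

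Finally, varied blocks do not make the last places impossible to deduce, as might be supposed. With the possible sizes known, about 1.9 remain certain and guessing hardly changes.

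**Conclusion.** The point holds as an avoidable design weakness, not as a demonstrated bias or a contradiction in the protocol. If one observer knows all earlier allocations, or each site fills its own list, up to about 4.8 of 48 allocations are certain in advance, 44% can be guessed correctly, and control is known to be exhausted for about 9. If two observers share a list and each sees only their own site, certainty is near 0 and control is known to be exhausted for about 1. The protocol does not settle which applies. That the trial is open is an inference from the visibly different arms and the absence of any described blinding. The importance is modest, but so is the cost of the remedy.

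**What to change.** Generate one permuted list of 48 with 12 per arm. Keep its structure out of the protocol and all site-facing documents, held only by the person who generates it. This preserves the planned group sizes and, even against a fully informed observer, leaves about 1.3 certain allocations, 36% correct guesses and 2.8 places after the last control.

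Undisclosed varied block sizes are a weaker alternative: they remove most of the certain allocations but leave guessing about where it is.

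The cost is one new list and a short edit to the allocation paragraph. The Ethics section still describes submission to the review board as to come; if no child has yet been enrolled, nothing else changes. The statistical downside is looser balance between arms during recruitment, or at the end if recruitment stops before 48.

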 - i. All groups (including control): 30 minutes
- 3. Week 24 (6 months)
 - g. All groups (including control): 1 hour at CCC-SLP and Dentist, total = 2 hours

Treatment timeline

- 1. Initial treatment consults involve educating patients on protocol - occurs 2 weeks after first measurement and successful eligibility screen
 - a. Myo Munchee ONLY group: 15 minutes
 - b. OMT ONLY group: 30 minutes
 - c. Myo Munchee + OMT group: 30 minutes
- 2. Every 2 weeks until week 10 (T10), 8 weeks after initial treatment appointment:
 - a. Myo Munchee ONLY group: 15 minutes
 - b. OMT ONLY group: 30 minutes
 - c. Myo Munchee + OMT group: 30 minutes
- 3. Every 4 weeks after T10 until week 26 (T26):
 - a. Myo Munchee ONLY group: 15 minutes
 - b. OMT ONLY group: 30 minutes
 - c. Myo Munchee + OMT group: 30 minutes

At home timeline

- 1. The exercises prescribed by the CCC-SLP will need to be completed at home outside of therapy appointments
- 2. The weekly and total time commitment over the 6 months
 - a. Myo Munchee ONLY - 6 days/week
 - i. Weekly: 72 minutes/week
 - ii. Total at home time commitment = 31 hours
 - b. OMT ONLY - 6 days/week
 - i. Weekly: 90 minutes OMT exercises.
 - ii. Total at home time commitment = 39 hours
 - c. Myo Munchee and OMT - 6 days/week
 - i. Weekly: 72 minutes Myo Munchee chewing, 90 minutes OMT exercises.
 - 1. Total = 2 hours, 42 minutes
 - ii. Total at home time commitment = 70 hours

Total Time commitment

Enrolling in the study is a 26-week commitment with variation in time commitments for each group.

- 1. Treatment groups
 - a. **Myo Munchee Only:**
 - i. Initial measurement consultation: 1 hour at dentist and CCC-SLP = 2 hours

- ii. T10 and T26 measurement appointments: 1 hour at dentist and CCC-SLP = 4 hours

- iii. Treatment appointments:

- 1. Before T10: 15 minutes every 2 weeks = 1 hour

- 2. After T10: 15 minutes every 4 weeks = 1 hour

- iv. Commitment outside of appointments: Weekly: 72 minutes/week. Total = 31 hours

- v. Total time commitment: approximately **39 hours**

b. Oral Motor Therapy ONLY:

- i. Initial measurement consultation: 1 hour at dentist and CCC-SLP = 2 hours

- ii. T10 and T26 measurement appointments: 1 hour at dentist and CCC-SLP = 4 hours

- iii. Treatment appointments:

- 1. Before T10: 30 minutes every 2 weeks = 2 hours

- 2. After T10: 30 minutes every 4 weeks = 2 hours

- iv. Commitment outside of appointments:

- 1. Oral Motor Therapy: 90 minutes/week. Total = 39 hours

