- v. Total time commitment: approximately **49 hours**

c. Myo Munchee and Oral Motor Therapy:

- i. Initial measurement consultation: 1 hour at dentist and CCC-SLP = 2 hours

- ii. T10 and T26 measurement appointments: 1 hour at dentist and CCC-SLP = 4 hours

- iii. Treatment appointments:

- 1. Before T10: 30 minutes every 2 weeks = 2 hours

- 2. After T10: 30 minutes every 4 weeks = 2 hours

- iv. Commitment outside of appointments:

- 1. Myo Munchee: 72 minutes/week. Total = 31 hours

- 2. Oral Motor Therapy: 90 minutes/week. Total = 39 hours

- v. Total time commitment: approximately **80 hours**

d. Control group

- i. Initial measurement consultation: 1 hour at dentist and CCC-SLP = 2 hours

- ii. T10 and T26 measurement appointments: 1 hour at dentist and CCC-SLP = 4 hours

- iii. Total time commitment: **6 hours**

Measurement and Treatment Timeline

Procedures		^Eligibility criteria screen Week 0 (T0)	Initial treatment consultation - week 2 (T2)	#Treatment Every 2nd week	Week 10 (T10)	#Treatment Every 4th week	Study Completion Week 26 (T26)
Informed Consent		X					
Assessment of Eligibility Criteria		X					
Therapy treatment protocol administration	Myo Munchee ONLY	X	X	X	X	X	X
	OMT ONLY	X	X	X	X	X	X
	Myo Munchee + OMT	X	X	X	X	X	X
	Control	X					
Clinical Measurements	*Patient History	X					
	**Dental	X			X		X
	**Orofacial Myofunctional Dysfunction	X			X		X
	Postural Assessment	X			X		X
	Ankyloglossia	X					X
Questionnaires	Sleep Disorders Inventory for Students - Revised	X			X		X
	***Compliance tracker	X			X		X
Additional data	Exit Interview						X
Adverse Events Evaluation				X	X	X	X

*Patient history form includes previous 3-day diet and medical history (included as part of Sleep Disorders Inventory for Students – Revised)

**Additional question to records any changes to the patient's activities, e.g. started chewing gum

***Compliance tracker: paper form will be completed each month by parent and upload to an online form

#After T10, the treatment appointments switch to every 4 weeks until T26

^Eligibility, Enrollment, Informed Consent, and Initial Data Collection will be performed when enrolled in the study. Treatment group allocation will be made after the patient meets all eligibility criteria.

Patient safety

1. Assessment of Safety Event Report Forms

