- Researching without the requisite approvals, permits or licenses required by laws, regulations, and disciplinary standards related to the responsible or safe conduct of research.
- Failure to conduct research as approved by an ethics review body where that conduct leads to (or has the potential to) results in participant harms.
- Any breaches as outlined in the US National Science Foundation Responsible and Ethical Conduct of Research conduct of research that leads to (or has the potential to) result in participant harms.

14. Reporting Protocol Deviations

- Protocol deviations occurring at a site must be documented in site files and reported to the Principal Investigator.
- The Principal Investigator must review the protocol deviation and the clinical trial protocol to establish the corrective actions and preventative steps to prevent the deviation from reoccurring.

15. Reporting of a Serious Breach

- A serious breach occurring at a participating site must be reported to the Principal Investigator within 72 hours.
- The Principal Investigator must review the serious breach, along with the clinical trial protocol, to develop a Corrective and Preventive Action (CAPA) that defines the steps to prevent the serious breach from reoccurring.

16. Review of a Protocol Deviation and a Serious Breach

- The Principle Investigator will review reports to establish whether the event meets the definition of a protocol deviation or serious breach, to establish whether the

proposed is appropriate and establish whether there is or will be an ongoing impact on the reliability and robustness of the data generated.

- Principle Investigator and Myo Munchee will seek advice from the approving IRB on the corrective and preventive action

Data Management and Software

Deidentification of data

1. Refer to this document for patient enrollment information - [link](#)
2. Patients will be assigned a code upon enrollment so that their information is de identified across all systems except for the clinics that they are receiving care
3. Case ID example: Ben Cook
 - a. First subject enrolled in the study: 01
 - b. First name: Ben
 - c. First 2 letters of last name: CO
 - d. Case ID: 01CO

Data Management

Patient data storage and disposal

- Data storage will be managed by Myo Munchee, SleepInventory.com a service of Child Uplift, Inc., and the Children's Airway Screen Taskforce (CGASP database)

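### The randomisation list is kept with the enrolment document, and the protocol does not prevent sight of later allocations while later children are still being screened

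*Protocol*

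**What the plan says.** The protocol's Method of treatment group allocation section names four arms and states "Permuted block randomization with block size = 12 will be carried out using the following shinyApps". It then says "The randomization list will be attached to the enrolment document and concealed from the investigators until patients are recruited". The object concealed is the list, and the event that ends concealment is recruitment.

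Four other places bear on this:

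- A footnote to the Measurement and Treatment Timeline table says "Treatment group allocation will be made after the patient meets all eligibility criteria".
- The Treatment timeline section says the initial treatment consult "occurs 2 weeks after first measurement and successful eligibility screen".
- The Deidentification of data section numbers children as they enter, with the example "First subject enrolled in the study: 01". It also says "Refer to this document for patient enrollment information", by a link whose target is not available here.
- The Treatment Groups section says that the therapist "for the treatment groups will see all 48 patients".

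The protocol names no holder of the list, no central allocation service, and no sealed or entry-by-entry release. It describes no blinding.

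**The concern.** Allocation concealment requires that whoever decides on the next child's entry cannot know the arm that child would receive. A list stored with the enrolment document, and concealed until recruitment, does not secure this once recruitment has begun.

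Some entry decisions leave room for judgement. Examples are daytime and night-time mouth breathing that need only be suspected, tolerance of the initial examination, and the screening item "Accepts Myo Munchee on first presentation". Someone who knew the next arm could pass, defer or decline a borderline child according to expected cooperation or prognosis. With 12 children per arm, a few such decisions could move an arm's mean. The arms also differ visibly (device, exercises, both, or nothing), so concealment before entry is one of the few protections available to this trial.

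**Working it through.** The protocol gives no figure for concealment, so the check is mainly a reading of its sections against each other.

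**1. The power statement is unaffected.** For 12 against 12, d = 1.2 and two-sided 5%, the noncentrality is 1.2 × √(12/2) = 2.94 on 22 degrees of freedom. Power is 80.2%, which agrees with the stated figure of at least 80%. Nothing below alters it.

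**2. When the list must be used.** Enrolment is sequential, because case numbers start at 01. Treatment starts two weeks after a child's own first measurement and screen, so a child's arm must be known by then. The first child's entry is therefore read no later than about two weeks after the first screen. Every child screened after that is assessed when the list has already been consulted. The only escape is to screen all 48 within about two weeks. The protocol gives no recruitment rate and does not plan for that.

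**3. Three readings of the concealment sentence.**

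- Concealed until all children are recruited: no exposure, but this does not fit step 2.
- Each entry concealed until that child is recruited: no exposure, but the text does not say this and gives no means of doing it.
- The list concealed until recruitment begins or a child is recruited: later entries are exposed.

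The table footnote does not decide between the second and third. It puts eligibility before allocation for the child in hand and is silent on entries for children not yet screened.

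**4. Size of the exposure.** If the full list is uncovered when the k-th child is recruited, the later allocations visible number 48 − k:

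| List uncovered at child | Later allocations visible |
|---|---|
| 1 | 48 − 1 = 47 |
| 12 | 48 − 12 = 36 |
| 24 | 48 − 24 = 24 |
| Single release throughout | 0 |

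The first row is the worst case, not an estimate.

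**5. A separate leak, for scale.** A fixed block of 12 over four arms holds 12/4 = 3 per arm, and 48/12 = 4 blocks. A recruiter who always guesses an arm with most places left in the block is right for about 5.29 of 12 allocations (simulation of 40,000 blocks). That is 5.29/12 = 44%, or 4 × 5.29 ≈ 21 of 48, against 12 of 48 by chance. This assumes one unstratified list with every past allocation seen by one recruiter, although two sites are listed. It comes from the published block size and would exist wherever the list was kept.

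**The case against.** A reader might infer that the screeners hold all 48 allocations from the first recruit onward. The protocol does not support that. It does not say that the full list is uncovered at once, and a child-by-child meaning is natural and agrees with the table footnote. The enrolment document is not shown. Nothing establishes that it is the linked document in the data section, that it is a clinic form, or that the dentist and therapist who do the T0 assessments hold it. This objection stands, and it limits the point to what the text permits.

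The room for steering is also narrower than the judgement items suggest. Every child needs at least two maxillary traits defined by millimetre cut-offs. Resting mouth posture is to be corroborated by video. Acceptance of the device is required before entry to any arm, so children who refuse it at first should be absent from all four. These points stand too. Deferral or selection by expected compliance or prognosis remains possible.

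A reader might also infer that any resulting bias would be beyond repair. That is too strong. Dental measurements are taken at T0, and the Data Analysis section allows adjustment for demographic and clinical variables, which could reduce measured imbalance. It could not reach unmeasured traits such as family motivation.

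Lastly, the 44% guessing rate should not be set against 47 of 48 as if both were estimates. One is a guessing strategy under stated assumptions and the other is a worst case.

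**Conclusion.** The point holds as a weakness in a mechanism that the protocol itself specifies. Who holds the list and when an entry is released are matters of trial conduct, so this is not something left to the analysis plan. As written, the text allows later allocations to be seen before later children are judged eligible, and no other section closes that gap.

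The consequence is a risk of selection bias, with no evidence that a leak has occurred. Between 0 and 47 later allocations could be visible, depending on how the sentence is carried out. The upper end requires the full list to be uncovered at the first recruit. The conclusion assumes that recruitment runs longer than about two weeks. If release child by child was intended, the protocol still needs to say so and say how. Block predictability is a separate matter that this conclusion does not rest on.

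**What to change.** Replace the concealment sentence in the Method of treatment group allocation section with wording to this effect:

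- The randomisation list is not attached to any enrolment document.
- It is held by a named role that does not screen, measure or enrol children.
- One allocation is released per child, only after consent, eligibility and T0 measurements have been logged with date and time.

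The holder can be an existing team member. The biostatistician is one choice, but the Data access section gives that role data only at study completion, so the duty during the trial would have to be added. A remote coordinator is another. The contacts section lists that role together with the principal investigator, so the wording should then make clear that concealment applies to everyone who screens, measures or enrols.

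The cost is a protocol wording change, one short message per child (48 in all) and a small added duty for one person. It should be in place before the first allocation, because steered enrolment cannot be undone afterwards. It brings visible later entries to 0 but does not address guessing from the fixed block of 12.
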